9.7.3 Intensity of Adverse Events

The maximum intensity of an AE during a day should be recorded on the eCRF. If the intensity of an AE changes over a number of days, then separate entries should be made having distinct onset dates for the changes in severity. The intensity of the AE will be graded by the Investigator using the following criteria as guidelines:

- Mild: AEs are usually transient, requiring no special treatment, and do not interfere with patient's daily activities.
- Moderate: AEs typically introduce a low level of inconvenience or concern to the patient and may interfere with daily activities, but are usually ameliorated by simple therapeutic measures.
- Severe: AEs interrupt a patient's usual daily activity and traditionally require systemic drug therapy or other treatment.

9.7.4 Causal Relationship to Study Product

The following criteria should be used in assessing the apparent causal relationship of an AE to study product:

Definitely - The AE:

- Follows a reasonable temporal sequence from study product administration.
- Abates upon discontinuation of the study product (de-challenge).
- Is confirmed by reappearance of the reaction on repeat exposure.

Probably - The AE:

- Follows a reasonable temporal sequence from study product administration.
- Abates upon discontinuation of the study product (de-challenge).
- Cannot be reasonably explained by the known characteristics of the patient's state.

Possible - The AE:

- Follows a reasonable temporal sequence from study product administration but that could readily be produced by a number of other factors.

CONFIDENTIAL PROTOCOL

An Evaluation of the Reduction in Erythema by RHOFADETTM (oxymetazoline hydrochloride) Topical Cream, 1% (Allergan) in Adult Patients with Moderate to Severe Persistent Facial Erythema Associated with Rosacea.

Unlikely - The AE:

- Follows a reasonable temporal sequence from study product administration.
- Could have been produced by either the patient's clinical state or by study product administration.

Not related - The AE:

- Does not have a reasonable temporal association with the administration of study product.
- Has some other obvious explanation for the event.

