9.7.8 Serious Adverse Events and Adverse Events Requiring Discontinuation

Non-serious events that require discontinuation of study product (including laboratory abnormalities) should be reported to Perrigo within one working day from reporting of the event by the Investigator.

Patients who discontinue due to AEs should be followed clinically until their health has returned to baseline status, or until all parameters have returned to normal. It is expected that the Investigator will provide or arrange appropriate supportive care for the patient.

A patient who experiences a severe AE related to study product will be discontinued from the study.

The notification about any SAE should be directed to the contact information provided in Section 9.7.6.

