**8.3.1 Adverse Events**

All the adverse events (AEs) reported throughout the study will be coded and classified according to the MedDRA (Medical Dictionary for Regulatory Activities) coding dictionary (Version 20.0 or higher). Each adverse event is to be evaluated for date of start and end, seriousness, severity, causal relationship with the study drugs, action taken and outcome.

All AEs will be listed by patient.

A summary table of the number and percent of patients with AEs by system organ class, preferred term will be presented. Each patient will be counted only once within each preferred term.

A frequency summary table of the number of AEs by system organ class, preferred term, severity will be presented. Severity will be classified as “Mild”, “Moderate”, or “Severe”.

Similarly, a frequency summary table of the number of AEs by system organ class, preferred term, and relationship to a study drug will be presented. Relationship to a study drug will be classified as “Not Related”, “Unlikely”, “Possible”, “Probably”, “Definitely”.

[REDACTED]

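### Protocol 9.7.4 does not separate 'Unlikely' from 'Possible', and an event with plausible timing, no other explanation and resolution during continued dosing fits none of the five causality labels

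*Protocol*

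**What the plan says.** Protocol 9.7.4 says its criteria should be used to assess causality, which is firmer than 9.7.3, where the intensity grades are offered as guidelines.

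- 'Possible' applies to an event that "Follows a reasonable temporal sequence from study product administration but that could readily be produced by a number of other factors".
- 'Unlikely' repeats the timing criterion and adds that the event "Could have been produced by either the patient's clinical state or by study product administration".
- 'Probably' and 'Definitely' both list plausible timing and abatement once the product is stopped. 'Probably' adds that the event "Cannot be reasonably explained by the known characteristics of the patient's state"; 'Definitely' adds that it "Is confirmed by reappearance of the reaction on repeat exposure".
- 'Not related' has two bullets: the event "Does not have a reasonable temporal association with the administration of study product", and it has another obvious explanation.

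Protocol 9.7.5 obliges the investigator to give a relatedness opinion on every AE. SAP 8.3.1 then specifies a frequency table of the number of AEs by system organ class, "preferred term, and relationship to a study drug will be presented", using the five labels. Protocol 9.7.8 uses relatedness as a yes/no condition: "A patient who experiences a severe AE related to study product will be discontinued from the study". It does not say which labels count as related.

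**The concern.** A causality scale has to give each event one label, and a rater reading 'Unlikely' should find something that makes the product an improbable cause. Here the definition names the product as a candidate on equal terms with the patient's condition. Two careful investigators, or one investigator on two days, could file the same event under different labels and both follow the text.

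The overlap falls where this study expects its AEs. Protocol 9.7 lists erythema, flushing, skin burning and warm skin among treatment-related reactions. In patients with facial erythema of rosacea, several of these could come from the disease or from the cream. The study has one product, is open-label and has no placebo, so no comparator arm helps with attribution, and the investigator's rating is the main evidence on it. At stake is whether the split between 'Unlikely' and 'Possible' in the SAP table carries information, and whether every event can be rated at all.

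**Working it through.** The plan gives no figure to reproduce, so the check is on the logic of the definitions. The criteria in Protocol 9.7.4, side by side:

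| Label | Plausible timing | Abates on stopping | Recurs on re-exposure | Other cause |
|---|---|---|---|---|
| Definitely | yes | yes | yes | not addressed |
| Probably | yes | yes | not addressed | no reasonable one |
| Possible | yes | not addressed | not addressed | could readily explain it |
| Unlikely | yes | not addressed | not addressed | could explain it, and so could the product |
| Not related | no | not addressed | not addressed | obvious one |

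**Coding.** There are six yes/no features: timing (T), abates on stopping (D), recurs on re-exposure (R), another factor or the clinical state could cause the event (O), the product could cause it (P), and another obvious explanation (X). Assumptions: R requires D; X implies O; bullets within a label apply jointly; and 'either … or' in 'Unlikely' means that both are candidate causes. The labels become:

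- Definitely = T, D and R
- Probably = T, D and not O
- Possible = T and O
- Unlikely = T, O and P
- Not related = not T, and X

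**Number of patterns.** D and R give 3 combinations. O, P and X give 6 (2 with O absent, 4 with O present). T gives 2. The total is 2 × 3 × 6 = 36.

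| Labels met | Patterns |
|---|---|
| none | 14 |
| Not related only | 6 |
| Possible only | 4 |
| Possible and Unlikely | 4 |
| Probably only | 2 |
| Definitely and Probably | 2 |
| Definitely and Possible | 2 |
| Definitely, Possible and Unlikely | 2 |

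**Overlap.** 'Unlikely' is met by 4 + 2 = 6 patterns, and all 6 also meet 'Possible'. No pattern is 'Unlikely' alone.

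**Gap.** With plausible timing and no de-challenge, 6 patterns remain: 2 meet 'Possible', 2 meet 'Possible' and 'Unlikely', and 2 meet nothing. In those last 2 no other cause is available, so 'Possible' and 'Unlikely' fail, and without D 'Probably' and 'Definitely' fail as well. The one that matters in practice is the pattern in which the product could have caused the event.

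**Sensitivity to the reading.**

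- The other 14 − 2 = 12 patterns without a label have no plausible timing and no obvious other explanation. If either bullet of 'Not related' is enough, those 12 become 'Not related'. The 2 with plausible timing still have no label.
- If 'either … or' means at least one of the two, 'Unlikely' becomes T and (O or P). All 4 + 4 + 2 + 2 = 12 'Possible' patterns then also meet 'Unlikely', so the overlap grows from 6 to 12. The gap pattern in which only the product is a candidate cause would then be called 'Unlikely', which is no improvement.

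**The case against.** Several objections have force.

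- **The SAP has no related/not-related split.** A reader might infer that one event could be tabulated as related or as not related. The readable text of SAP 8.3.1 keeps five levels and lists all AEs by patient, so a shift between 'Unlikely' and 'Possible' stays visible. With its bullets read jointly, 'Not related' excludes any event with plausible timing. The stronger reading needs a cut that neither document states. Redacted text could hold a pooling rule, but that would not repair the definitions.
- **No rate can be attached.** The relationship table counts AEs. The table of numbers and percentages of patients is by system organ class and preferred term only. A swing in the percentage of patients with related events would rest on an assumed cut and on a statistic the SAP does not describe.
- **De-challenge is often observable.** A reader might infer that patients who keep dosing can never have an event rated 'Probably' or 'Definitely'. That is too strong. The last dose is at Visit 4, and Protocol 9.7.5 follows AEs until resolved or for 30 days after final treatment, so an event persisting to the last dose can show abatement. A reaction that fades between daily applications and returns could arguably count as recurring on repeat exposure. What remains is the event that resolves during continued dosing.
- **No direction of bias is shown.** Every 'Unlikely' pattern also meets 'Possible', so an investigator may rate upward as easily as downward. The documents do not support a claim that the profile will look cleaner than it is.
- **Urgent reporting mostly bypasses the scale.** Serious or unexpected AEs go to the sponsor within 24 hours (Protocol 9.7.6), and SAEs during the study go to the IRB whatever their assessed causality (11.2.9). This limits the safety reach. One exception is Protocol 9.7.10.2, where reporting of SAEs arising after the last assessment depends on the investigator's causality judgement.

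These points narrow the consequence. They do not make 'Unlikely' distinguishable from 'Possible' or close the gap.

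**Conclusion.** The point holds as a defect in a stated rule, limited to three things. 'Unlikely' cannot be told apart from 'Possible', so the same AE can be counted at either level of the SAP 8.3.1 table. An event with plausible timing, no alternative explanation and resolution during continued dosing has no label. Protocol 9.7.8 relies on 'related' without linking it to the scale.

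The size can be stated only in logical terms: 6 of 6 'Unlikely' patterns are also 'Possible', and 2 patterns with plausible timing have no label. This rests on reading the bullets jointly and on treating the patient's clinical state as one of the other factors. The overlap and the lack of a sound label for the gap event survive the alternative readings tested. How many of the approximately 50 patients would be affected cannot be derived from the documents.

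**What to change.** Before any AEs are rated, reword Protocol 9.7.4 and any matching eCRF guidance so that each event fits exactly one label:

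- Give 'Unlikely' a criterion that makes the product improbable: doubtful timing, or another cause judged more likely than the product.
- Keep 'Possible' for plausible timing where product and other factors are both plausible and the other factor is not judged the more likely.
- In 'Probably', ask for abatement only where the product was stopped, and say where an unexplained event belongs if the product was stopped and it did not abate.
- Say whether 'Not related' needs one or both of its bullets, and that an event meeting 'Definitely' takes that label.

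If the report will pool levels into related and not related, state the pooling in SAP 8.3.1, for tabulation only. Protocol 9.7.8 must be reconciled with 9.7.4 so that 'related' has a defined meaning there; which levels should lead to discontinuation is a clinical decision and is not proposed here.

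The cost is minor wording in the protocol, eCRF guidance and SAP, with no new data or visits. Some events may move from 'Unlikely' to 'Possible' or 'Probably'. The change needs to come first, because ratings made under overlapping labels cannot be reliably separated later.

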9.7.5 Eliciting and Reporting of Adverse Events

The Investigator will periodically assess patients for the occurrence of AEs. To avoid bias in eliciting AEs, the patient or parent/legally authorized representative should be asked a non-specific question (e.g., "How have you been feeling since your last visit?") to assess whether any AE has been experienced since the last visit. All AEs (as defined in Section 9.7.2), either observed by the Investigator or one of his/her medical collaborators, or reported by the patient spontaneously or in response to direct questioning, will be reported and documented in the source and eCRF. When reporting an AE, the Investigator must assign a severity grade to each event and declare an opinion on the relatedness of the event to the study product or procedure.

Adverse events will be documented in source and recorded in a timely manner on eCRF. Adverse events that are identified at the last assessment visit (or the early termination visit) must be recorded on the AE page of the eCRF with the status of the AE noted.

Adverse event reporting begins from the signing of informed consent/assent. Worsening of erythema of rosacea from baseline may be expected, however, if the conditions worsens to the degree that it requires alternative treatment or results in discontinuation from the study, it shall be recorded as an AE and will be documented on the patient's source documents and on the eCRF. Adverse events should be followed until resolved or 30 days after the final study treatment. In any case, SAEs that are not resolved or considered to be chronic within 30 days of the final study treatment must be followed by the Investigator until they become resolved or are considered to be chronic (stabilized for at least 30 days). All events that are ongoing at this time will be recorded as ongoing on the eCRF.

9.7.6 Expedited Reporting Responsibilities of the Study Center

For any serious or unexpected AE, Perrigo must be notified within 24 hours of when the Investigator first learns of the occurrence of the event. Expedited reporting requirements for SAEs are described below. Adequate information must be collected with supporting documentation to complete a standard report for submission to the sponsor. The AE term on the AE eCRF and the SAE report should agree exactly. Special attention should be given to recording hospitalizations and concomitant medications.

CONFIDENTIAL PROTOCOL

An Evaluation of the Reduction in Erythema by RHOFADETTM (oxymetazoline hydrochloride) Topical Cream, 1% (Allergan) in Adult Patients with Moderate to Severe Persistent Facial Erythema Associated with Rosacea.

Patients with unresolved AEs or SAEs should be followed by the Investigator until the events are resolved, events determined to be chronic, or the patient is lost to follow-up according to Section 9.7.5. Resolution means the patient has returned to the baseline state of health, or the Investigator does not expect any further improvement or worsening of the AE. The Investigator should continue to report any significant follow-up information to Perrigo up to the point that the event has resolved.

All SAEs will be reported as per applicable regulations. All SAEs encountered during the study will be reported on the appropriate form and summarized in the final report.

Any SAEs should be reported [REDACTED] within 24 hours. Following is the contact information:

[REDACTED]

[REDACTED]

[REDACTED]

[REDACTED] will report any SAE to Sponsor:

Documentation of serious or unexpected AEs and follow-up information should be sent to the Sponsor within 24 hours from [REDACTED] being made aware of the SAE. Following is the contact information:

[REDACTED]

CONFIDENTIAL PROTOCOL

An Evaluation of the Reduction in Erythema by RHOFADETTM (oxymetazoline hydrochloride) Topical Cream, 1% (Allergan) in Adult Patients with Moderate to Severe Persistent Facial Erythema Associated with Rosacea.

The sponsor will be responsible for notifying the FDA of any SAEs. The sponsor must notify FDA of fatal or life-threatening SAE as soon as possible, but no later than seven calendar days from reporting the event by the Investigator.

9.7.7 Submitting an Expedited Safety Report to the IRB

Once [REDACTED] receives all supporting documentation for the reported event, the Medical Monitor, in conjunction with Perrigo, will determine if the safety report is eligible for expedited review. [REDACTED] will log the initial event and will notify Perrigo that an event has been reported within one business day after initial receipt. [REDACTED] will complete the review of the event, enter information into their safety database, and generate the report. This form, as well as other supporting documentation, will be forwarded to [REDACTED] Medical Monitor for review. [REDACTED] will finalize the report and distribute it to Perrigo within two days after initial receipt. When expedited safety reporting to regulatory authorities is indeed required, the Investigator should review and update any newly available materials at once. Follow-up queries may be sent to the study center to further clarify the event.

Each expedited safety report will routinely include a brief cover memorandum, the completed report, and any additional pertinent information recommended by [REDACTED], Perrigo, or study Medical Monitor. Once the report is assembled, the Principal Investigator must submit the expedited safety report to the IRB within the required reporting timeframe. Follow-up reports should be submitted when requested or when pertinent information becomes available.

9.7.8 Serious Adverse Events and Adverse Events Requiring Discontinuation

Non-serious events that require discontinuation of study product (including laboratory abnormalities) should be reported to Perrigo within one working day from reporting of the event by the Investigator.

Patients who discontinue due to AEs should be followed clinically until their health has returned to baseline status, or until all parameters have returned to normal. It is expected that the Investigator will provide or arrange appropriate supportive care for the patient.

A patient who experiences a severe AE related to study product will be discontinued from the study.

The notification about any SAE should be directed to the contact information provided in Section 9.7.6.

9.7.9 Pregnancy

CONFIDENTIAL PROTOCOL

An Evaluation of the Reduction in Erythema by RHOFADETTM (oxymetazoline hydrochloride) Topical Cream, 1% (Allergan) in Adult Patients with Moderate to Severe Persistent Facial Erythema Associated with Rosacea.

A negative result of a urine pregnancy test having a minimum sensitivity of at least 50 mIU/mL for hCG should be obtained, before study participation. Pregnancy testing will be performed at Visits 1, 2, and 4 and the results of all pregnancy tests (positive or negative) will be documented.

At the time an Investigator or site personnel becomes aware that a patient became pregnant following study participation, the Investigator or designee will report the pregnancy immediately by phone and by faxing a completed Pregnancy Report to [REDACTED] within one working day after being notified of the pregnancy report.

The report will include the following elements:

- Patient's (mother's) coded study identifier;
- Date of patient's last menstrual period;
- Total accumulated dose of study product administered to date;
- Date of study product administration.

The pregnancy will be reported as an AE. The Investigator will follow the patient until completion of the pregnancy and must assess the outcome in the shortest possible time but not more than 30 days within completion of the pregnancy.

Upon delivery, miscarriage or abortion, the Investigator or designee must forward a follow-up Pregnancy Report with any relevant information on the present condition of the fetus to the [REDACTED], including:

- Mother's coded study identifier(s);
- Gestational age at delivery, miscarriage or abortion;
- Birth weight, gender, length and head circumference, if available;
- Apgar scores recorded after birth, if available;
- Any abnormalities.

If the outcome of the pregnancy meets the criteria for immediate classification of an SAE (e.g., spontaneous or therapeutic abortion [any congenital anomaly detected in an aborted fetus is to be documented], stillbirth, neonatal death, or congenital anomaly), the Investigator will report the event by phone and by faxing a completed SAE report form to [REDACTED] within one working day after being notified of the pregnancy report.

If [REDACTED] responsibilities for the trial are completed before the outcome of the pregnancy is known, they must have a plan in place to conduct pregnancy outcome follow-up and notify Perrigo.

CONFIDENTIAL PROTOCOL

An Evaluation of the Reduction in Erythema by RHOFADETTM (oxymetazoline hydrochloride) Topical Cream, 1% (Allergan) in Adult Patients with Moderate to Severe Persistent Facial Erythema Associated with Rosacea.

9.7.10 Post-Study Adverse Events

9.7.10.1 Non-Serious Adverse Events

Adverse events that are identified at the last assessment visit (or the early termination visit) must be recorded on the AE eCRF with the status of the AE noted.

9.7.10.2 Serious Adverse Events

Adverse events that are identified at the last assessment visit (or the early termination visit) must be recorded on the AE eCRF with the status of the AE noted.

Serious adverse events that are identified on the last assessment visit (or the early termination visit) must be recorded on the AE eCRF and reported to Perrigo according to the procedures outlined above. Patients with unresolved previously reported SAEs, or any new SAEs identified on the last assessment visit, should be followed by the Investigator until the events are resolved, or the patient is lost to follow-up according to Section 9.7.5. Resolution means the patient has returned to the baseline state of health, or the Investigator does not expect any further improvement or worsening of the AE. The Investigator should continue to report any significant follow-up information to Perrigo up to the point that the event has resolved. Any SAE reported by the patient to the Investigator that occurs after the last assessment, and are determined by the Investigator to be reasonably of the use of the study product, should be reported to Perrigo.

